#### Exclusion Criteria:

- Women who are currently pregnant or planning on becoming pregnant
- Adults lacking the capacity to consent
- Patients referred to HIV care outside of Johns Hopkins and/or BCHD STD clinics
- Patients with estimated creatinine clearance <30 mL/min at last documented laboratory testing in the available medical record at site of referral, self-report of

chronic kidney disease without documented creatinine within the last three months

- Patients judged by clinic or study staff to be physically or emotionally unable to provide consent or participate in all study procedures

### 3. Drugs/ Substances/ Devices

Prescriptions for at least fourteen days of the antiretroviral medication regimen chosen by the prescribing provider will be prescribed and dispensed to participants. These FDA-approved drugs will be used according to the FDA-approved indication. Providers in the JGBSP and BCHD HIV clinics have expertise in prescribing antiretroviral medications and caring for HIV-infected patients and they will take into consideration adverse drug-drug interactions with other patient medications and patient comorbidities when choosing the starter pack of antiretroviral medications as per standard of care.

### 4. Study Statistics

*Measures and Outcomes*

Demographic and psychosocial information; barriers, facilitators and acceptability of HIV treatment and RHTI:

Table 1. Patient survey instruments and time of collection (Appendix 1)

Domain	Instrument	Collection	
		Baseline	Week 4
Substance use			
Drug use	NIDA ASSIST	X	X
Alcohol use	AUDIT-C	X	X
Mental health			
Depression and panic	PHQ-8 and PHQ-A	X	X
Quality of life	EuroQOL-5D	X	X
Psychosocial			
Social support	MOS-4	X	X
HIV stigma	HIV stigma scale (Earnshaw) 	X	X
Self-efficacy	HIV-related self-efficacy (Johnson) 	X	X
HIV knowledge			
HIV knowledge	ART knowledge questionnaire (Balfour, modified) 	X	X
Adherence			
Medication adherence	ACTG adherence questionnaire: AACTG, VAS, SRS	X	X
Barriers to medication and appointments	Barriers and facilitators to adherence questionnaire (derived from Yehia, et al) 	X	X
Patient satisfaction			
Patient satisfaction with clinic and HIV care linkage team	Patient satisfaction questionnaire (modified from Dang, et al) 		X

Demographics			
Demographic survey	NIDA Seek, Test, Treat and Retain for Vulnerable Populations: Data Harmonization Measure 	X	X
Prior HIV treatment history*			
History of past HIV treatment	JGBSP-ED linkage to care intake (selected questions)	X	

\*For patients previously diagnosed with HIV only

### **RHTI acceptability**

- number of patients offered RHTI, number of patients who accept RHTI
- number of patients who receive RHTI.

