### *Patient recruitment*

We will utilize existing HIV linkage to care services for newly and previously diagnosed patients identified at the Johns Hopkins East Baltimore campus, the JGBSP clinic and at the BCHD STD clinics to explore the feasibility and acceptability of RHTI in these settings. All patients identified in the Hopkins ED, Johns Hopkins inpatient HIV service, the JGBSP clinic and BCHD STD clinics who are newly diagnosed with HIV (test positive by 3rd or 4th generation HIV test or detectable HIV viral load with no previously documented positive HIV test by medical record and/or self-report) and patients with previous HIV diagnosis but by self-report are not in care and not on ART (> six months without HIV care and ART) will be referred to the Rapid HIV treatment initiation, Access and Engagement in care (RHAE) Research Assistant (RA) by call or text to a dedicated smart phone. At the time they are identified as needing a referral for HIV treatment services, a brief description of the study will be given to potentially eligible patients and a referral to the RHAE RA will be made with patient permission. In the ED, this referral will be made by ED HIV testing team members and/or ED clinicians. In the JGBSP clinic, the referral will be made by social work staff, nurses and/or medical providers. In the BCHD STD clinics, referrals will be made by patient advocates and/or medical providers. The linkage team will provide linkage services as per usual. In situations when potentially eligible patients present for clinical care when a Project RHAE staff member is not available to accept a referral and/or leave the clinical area before learning about the study, referring providers and staff who engage with the patient for treatment after the initial interaction will present the study and elicit interest and permission for referral at a later date in person or by phone. This may include patients who have been hospitalized at Johns Hopkins Hospital in which case the study team will discuss potential enrollment with the inpatient care team prior to approaching the patient for consent.

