### *Patient consent, survey administration*

After referral to the RA, the RA will describe the study to the patient and assess patient eligibility. A study clinician will confirm patient eligibility and the RA will consent patients who wish to enroll. Once consented, the RA will collect contact information and administer a standardized enrollment survey (Table 1). A tablet or computer will be used to record survey responses which will be uploaded to a secure REDCap Database. Domains assessed include illicit drug and alcohol use, depression and panic symptoms, stigma, quality of life, HIV knowledge and social support. The survey will assess anticipated barriers and facilitators to HIV care and adherence to medication and acceptability of RHTI. Date, time and location of HIV clinic follow up will be noted. To ensure adequate ability to obtain follow up information, patients referred to HIV care outside of Johns Hopkins and/or BCHD STD clinics will not be eligible for enrollment.

If the patient is eligible but declines enrollment, he or she will be offered enrollment in the survey-only study of RHTI (IRB00110075). A log of potentially eligible patients

who are not enrolled in the study will be kept by the Project RHAE study staff. This log will be kept in a secure Johns Hopkins network data base and will not include protected health information. The log will include: age, clinical site, whether the patient was newly or previously diagnosed, HIV risk factor, reason patient did not enroll, and if the patient enrolled in the survey-only study. Protected Health Information of patients referred by clinical staff who are not eligible or choose not to consent to enrollment will be destroyed.

*Implementation of RHTI protocol at the Johns Hopkins ED and JGBSP clinic*

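### Do the unnamed acceptability items in Table 1 and the undefined offer and acceptance counts leave RHTI acceptability unmeasured?

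*Protocol*

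**What the plan says.** The Patient recruitment section gives the purpose as "to explore the feasibility and acceptability of RHTI in these settings". Acceptability is approached in two ways.

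- **Survey.** Patient consent, survey administration states: "The survey will assess anticipated barriers and facilitators to HIV care and adherence to medication and acceptability of RHTI". The heading over Table 1 in section 4, Study Statistics, repeats it: "Demographic and psychosocial information; barriers, facilitators and acceptability of HIV treatment and RHTI". Table 1 refers the reader to Appendix 1 for the instruments.
- **Counts.** RHTI acceptability lists the "number of patients offered RHTI, number of patients who accept RHTI", followed by the number who receive RHTI.

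Two procedures feed the counts. Under Patient recruitment, clinical staff briefly describe the study to potentially eligible patients, and "a referral to the RHAE RA will be made with patient permission". Under Patient consent, survey administration, a log of potentially eligible patients "who are not enrolled in the study will be kept by the Project RHAE study staff". It holds no protected health information, and its fields include the "reason patient did not enroll, and if the patient enrolled in the survey-only study". That section adds: "If the patient is eligible but declines enrollment, he or she will be offered enrollment in the survey-only study of RHTI".

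**The concern.** Acceptability is one of the two things the study sets out to explore, and the routes to measuring it look thin.

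First, the text promises survey items on acceptability of RHTI, but no Table 1 row carries that label. The nearest rows cover barriers to medication and appointments, and week-4 satisfaction with the clinic and linkage team.

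Second, RHTI is described only for patients who have already consented to the research. Without a separate definition, accepting RHTI could be read as agreeing to the study, with its surveys, payments and chart review. A patient who wanted rapid treatment but no research would then count as a refusal of RHTI.

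Third, referral needs the patient's permission and the log is kept by study staff. A patient who refuses at the clinician's desk may never reach the log. If such patients drop out of the denominator, the acceptance proportion rises. No later analysis can recover a question that was not asked or a refusal that was not recorded.

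**Working it through.** **Survey against Table 1.** The rows are drug use, alcohol use, depression and panic, quality of life, social support, HIV stigma, self-efficacy, HIV knowledge, medication adherence, barriers to medication and appointments, patient satisfaction, demographics, and prior HIV treatment. That is 13 rows, and 0 name RHTI acceptability. The table lists instruments, not items. The barriers questionnaire is described as derived from a published source, and the satisfaction questionnaire as modified from one, so either could carry study-specific questions. Appendix 1 would settle this and is not shown. The established fact is that no row label names acceptability. It is not established that the items are absent.

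**Counts against procedures.**

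| Count | What the procedures give |
|---|---|
| Offered | No separate event is defined; staff describe the study |
| Accept | No event is defined apart from consent |
| Receive | Prescription and starter pack at an intake visit within one week of consent |

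Receipt is therefore distinct from consent. Because the intake can fall up to a week later, receipt among consenters can also vary. The number started on ART is listed separately under HIV linkage and care outcomes.

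**Log against referral.** The log's scope is potentially eligible patients who do not enroll. A patient who refuses referral fits that description. The log carries no protected health information, so withheld permission does not by its terms keep the patient out. The reason field can separate refusal of rapid treatment from refusal of research. What is unstated is how referring staff pass the entry to study staff.

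**Can a size be given?** Inputs: 32 identified and 67% participation (Sample Size and Analysis).

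- Participants: 32 × 0.67 = 21.44, about 21. Non-participants: 32 − 21 = 11, or 34.4%.
- Study Procedures instead gives 32 as projected enrollment. On that reading 32 / 0.67 = 47.8, about 48 identified, and 48 − 32 = 16 non-participants, or 33.3%. The share is nearly the same. The conflict between the two uses of 32 is a separate matter.
- If r refusers are missing from the denominator, the proportion is 21 / (32 − r). Every r above 0 is an assumption.

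| r (assumed) | Proportion | 95% Clopper-Pearson interval |
|---|---|---|
| 0 | 21/32 = 65.6% | 46.8% to 81.4% |
| 3 | 21/29 = 72.4% | 52.8% to 87.3% |
| 8 | 21/24 = 87.5% | 67.6% to 97.3% |
| 11 | 21/21 = 100% | 83.9% to 100% |

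The range runs from no effect to the largest possible one, and the documents do not say at which step non-participants leave. The numerator is also study participation, because 67% is a participation rate. The table shows how sensitive a participation proportion is to its denominator. It does not estimate error in RHTI acceptance. With the log kept as described, r = 0.

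**The case for a change.** The strongest case for a change is that these are data-capture points, not analysis choices. A statistical analysis plan can define a denominator, but it cannot supply an unasked question or an unlogged refusal. The reason field has no coding, there is no field for whether RHTI was offered, and the log holds no identifiers through which a reason could be recovered later. The survey-only study reaches only patients found eligible who decline enrollment and then agree to it. The number of referrals to the linkage team might offer a wider denominator, but it does not record whether RHTI was offered, and chart extraction is described as following enrollment. With about 21 to 32 participants, a few missing refusals would move a proportion visibly.

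Much of this stands as description: the two count definitions and the reporting step are not written down. It does not show that the plan as written goes wrong. The log's stated scope takes in referral refusers, a free-text reason can be classified afterwards, and the missing survey items are only inferred from row labels. The statement that all identified patients will be referred, followed by the condition of permission, reads as an ordinary qualification and not a contradiction.

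**Conclusion.** The observations are accurate, but the concern does not call for a change. Table 1 names no acceptability row, offer and acceptance lack their own definitions, and the route from referring staff to the log is unstated. Each is a gap that study staff and analysts can fill sensibly within the existing text: the appendix may hold the items, the intake visit identifies receipt, and the log already covers non-enrolled patients with their reasons.

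The size of any bias cannot be stated. Shifts such as 65.6% to 72.4% rest on assumed refusal counts and substitute study participation for acceptance of rapid treatment, so they carry no weight as evidence.

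This conclusion assumes that the log is kept to its stated scope, including patients who refuse referral, and that the reason is taken down when the patient declines. It also assumes that Appendix 1 holds the acceptability items the text promises. If Appendix 1 has none, the survey statement would be unsupported and acceptability would rest on the counts and the log.

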### **HIV linkage and care outcomes (Appendix 2):**

- number of referrals to linkage team
- number of patients who accept linkage services
- number of patients who complete initial HIV clinic appointment and time to appointment completion
- number of patients started on ART
- number of patients who achieve an undetectable HIV viral load time to ART initiation and time to achieve undetectable HIV viral load (<200 copies)
- baseline creatinine
- baseline genotype
- number of patients remain on ART through the end of the study
- number of patients who achieve an undetectable HIV viral load, time to ART initiation
- time to achieve undetectable HIV viral load (<200 copies)

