Patients recruited from the Johns Hopkins ED and/or JGBSP clinic social work will complete his/her ED/social work visit and will then be seen in the JGBSP clinic by a JGBSP clinic clinician for a medical HIV intake visit and prescription with receipt of ART starter pack. Patients recruited from the BCHD STD clinics will see be seen in the BCHD STD by a clinician for medical intake visit and prescription and receipt of ART starter pack. The clinicians who evaluate patients and initiate treatment will be those who provide continuity HIV care in the clinics. The date and time of the medical visit to initiate treatment at JGBSP clinic and BCHD STD clinic will be as soon as possible and the visit may occur as soon as immediately after recruitment (which is preferable) or may occur on a day other than the day of recruitment if the initial encounter occurs while the clinic is closed, is too late in the day to complete before clinic closes or patient prefers an appointment at a later date. The medical intake will take place no more than one week after consent is obtained. The intake will be as per usual in the JGBSP and BCHD HIV clinics. The following clinical labs will be obtained at the time of enrollment, as part of standard of care: CD4 count, HIV viral load, HIV genotype, CBC, comprehensive metabolic panel, urinalysis, viral hepatitis, syphilis serologies, GC/CT screening based on risk. As part of standard of care, clinicians and/or clinic staff (registered nurse, pharmacist) provide counseling on medication education, potential side effects and adherence. ART prescriptions will be written for at least 14 days of an antiretroviral medication regimen chosen at the discretion of the prescribing provider. Prescriptions for more than 14 days of medication can be prescribed at the discretion of the prescribing provider. Providers in the JGBSP and BCHD HIV clinics have expertise in prescribing antiretroviral medications and caring for HIV-infected patients and they will take into consideration adverse drug-drug interactions with other patient medications and patient comorbidities when choosing the starter pack of antiretroviral medications as per standard of care. Providers will also educate patients about the antiretroviral regimen and dosing recommendations as per standard of care. Pill boxes will be offered with each starter pack. At each clinic, patients are provided with 24/7 clinic contact information should he/she experience adverse side effects to medication and/or experience a medical emergency. Prescribing providers are responsible for reviewing the laboratory results and will follow up with the patient on any regarding any abnormalities requiring urgent/emergent medical attention including need to discontinue antiretroviral medication due to contraindications to a component in the regimen such as estimated creatinine clearance <30 mL/min (a contraindication with tenofovir alafenamide) or due to HIV resistance to a component of the antiretroviral regimen. Medical follow up will be scheduled within two to four weeks.

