## **2. Inclusion/Exclusion Criteria**

### *Patient Eligibility*

#### Inclusion Criteria:

- Men and women 18 to 65 years of age
- English speaking
- Patients identified in the Hopkins ED, Hopkins JGBSP clinic or BCHD STD clinics who are newly diagnosed with HIV (test positive by 3rd or 4th generation HIV test or detectable HIV viral load with no previously documented positive HIV test by medical record and/or self-report) and patients with previous HIV diagnosis but by self-report are not in care and not on ART (> six months without HIV care or ART)

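### Could patients already below 200 copies at enrolment be counted as having achieved viral suppression?

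*Protocol*

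**What the plan says.** **Outcome.** Section 4, under HIV linkage and care outcomes, lists a count of patients reaching an undetectable viral load and the "time to achieve undetectable HIV viral load (<200 copies"). The count and the time each appear twice in the list, which is a clerical repetition. No denominator, time origin or rule for patients already below the threshold is given. The heading refers to Appendix 2, the chart-review material, which is not at hand.

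**Entry.** Section 2, Inclusion Criteria, admits newly diagnosed patients who "test positive by 3rd or 4th generation HIV test or detectable HIV viral load with no previously documented positive HIV test", where the absence of an earlier positive test may come from the medical record, from self-report, or both. It also admits "patients with previous HIV diagnosis but by self-report are not in care and not on ART". The exclusion criteria contain no viral-load condition.

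**Baseline measurement.** Section 1, on implementing the RHTI protocol, states: "The following clinical labs will be obtained at the time of enrollment, as part of standard of care: CD4 count, HIV viral load", followed by the genotype and other tests. The same section gives 48 weeks of chart review after enrolment for the care outcomes.

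**The concern.** Eligibility does not guarantee viraemia at 200 copies or more. Three kinds of patient could start below the threshold:

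- someone taking ART who does not disclose it;
- someone who controls the virus without treatment;
- someone whose positive screening test was false.

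The route through a detectable viral load does not close the gap, because no level is attached to it. The gap in care is also worded in two ways: "> six months without HIV care or ART" in the Inclusion Criteria and "> six months without HIV care and ART" under Patient recruitment. Read literally, the first could admit a patient long out of care who stopped ART only recently and is still suppressed.

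Such a patient's enrolment sample already meets the only stated threshold. If it were taken as the event, the patient would count as a success of rapid initiation with a time of zero. The error can only flatter the strategy, and no control arm is described that would share it. This matters because Section 6 says the study could show that early ART improves clinical outcomes and reduces transmission, and suppression is the listed outcome closest to that statement.

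**Working it through.** The protocol gives no suppression rate, no share below 200 at baseline and no analysis set, so there is no planned figure to reproduce for this outcome. What can be done is to size the effect under stated assumptions and then ask whether the text prescribes the harmful scoring.

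**Inputs**
- Number of patients, N. Section 1 projects 32 enrolled. Section 4 (Sample Size and Analysis) has 32 identified and 67% participating, and 32 × 0.67 = 21.4. These figures do not agree, which is a separate matter, so both N = 21 and N = 32 are used.
- Number already below 200 at baseline, k. Not in the protocol; assumed 1, 3 or 5.
- True proportion suppressed among the rest, p. Not in the protocol; assumed 0.6 to 0.8.

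**Overstatement if all k are counted as successes**

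Reported proportion = [p(N − k) + k] / N

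Overstatement = reported − p = k(1 − p) / N

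| N | k | p = 0.8 | p = 0.6 |
|---|---|---|---|
| 21 | 1 | 1.0 points | 1.9 points |
| 21 | 3 | 2.9 | 5.7 |
| 21 | 5 | 4.8 | 9.5 |
| 32 | 1 | 0.6 | 1.2 |
| 32 | 3 | 1.9 | 3.7 |
| 32 | 5 | 3.1 | 6.2 |

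If these patients were scored at day 0, the time-to-suppression curve would start with a step of k/N: 1/32 = 3% for one patient among 32, and 3/21 = 14% for three among 21.

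**Chance that the question arises**

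P(at least one) = 1 − (1 − q)^N, where q is the chance that an enrolled patient is below 200 at baseline (assumed):

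| q | N = 21 | N = 32 |
|---|---|---|
| 2% | 35% | 48% |
| 5% | 66% | 81% |
| 10% | 89% | 97% |

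**Comparison with sampling error**

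At a true proportion of 0.7, the 95% half-width is 1.96 × √(0.7 × 0.3 / N). This is 19.6 points for N = 21 and 15.9 points for N = 32.

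**Does the text prescribe the scoring?**

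Set the outcome beside the laboratory schedule. The outcome speaks of patients who *achieve* the threshold and of the time taken to do so. The ordinary meaning is a move from unsuppressed to suppressed, and a patient who starts below 200 makes no such move. The enrolment viral load shows who these patients are. Nothing in the protocol says that the denominator is everyone enrolled, or that the enrolment sample can itself be the event.

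**The case for a change.** The best case for a change is that both halves of the problem are fixed in the protocol. Entry criteria cannot be altered by a statistical analysis plan, and the outcome carries its threshold here without a baseline condition. The outcome list names baseline creatinine and genotype but not baseline viral load, so its extraction is not assured by the visible text. The bias has one direction, at least one affected patient is quite likely even at a 5% share, and a sentence of clarification would be cheap.

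Part of this stands. The protocol sets no viral-load minimum, and the handling of patients below 200 is unwritten. A short definition would be tidier.

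The rest is weaker.

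- **Safeguards at entry.** The newly diagnosed route requires a diagnosis of HIV; nothing says that one unconfirmed screening result is enough. Section 1 has a study clinician confirm eligibility, and the medical record may be used to check for earlier positive tests. Table 1 in Section 4 has prior treatment history collected at baseline from previously diagnosed patients. The differing wording of the care gap follows, in both places, a main clause that requires the patient to be neither in care nor on ART.
- **Availability of the baseline value.** It is drawn as routine care and sits in the record that is reviewed for the outcomes. Whether the result is back before ART starts has no bearing on how the outcome is later analysed.
- **Large effects need extreme assumptions.** An overstatement of 12 points requires 30% below 200 at baseline with true suppression of 60%: 0.30 × (1 − 0.60) = 0.12. That is about 6 of 21 or 10 of 32 patients already suppressed despite being newly diagnosed or reporting no ART.
- **A restricted denominator has a cost.** The list runs as a care cascade from referral through linkage and ART start to suppression. Removing patients only at the last step breaks the common denominator, so a restricted count is an additional display and not a plain improvement.

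**Conclusion.** No change to the plan follows. The gap is real but small: entry does not require 200 copies or more, and the suppression outcome has no stated at-risk set or time origin. The protocol does not say that patients already below 200 are successes at time zero, and the natural reading of the outcome leaves them out. Such rules are commonly set in a statistical analysis plan or in the extraction material, neither of which is at hand. An analyst with the enrolment viral load would be expected to report these patients separately and to compute time to suppression among those who started at 200 or more.

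The size of any overstatement cannot be derived from the protocol. It would be about 0.6 to 1.9 points per affected patient, assuming true suppression of 60% to 80%, 21 to 32 patients, and the least favourable scoring. That is well inside the sampling error of one descriptive count in a study of feasibility and acceptability with no hypothesis test or success threshold. The conclusion would be different if the analysis plan took the enrolment sample as the event, or if a large share of patients proved to be below 200 at baseline and were not reported as such.
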